Precautions will be taken to maintain confidentiality of patient records and personal information. Raw data (pre-operative and post-operative measurements and operative report) will be maintained as part of the patient's confidential medical record, in accordance with University, state and federal guidelines. Study data will be compiled into an electronic file by the investigators and maintained on a password-protected network. Data entries will be coded by patient identification number. Any reports of the results of this study that are published or presented will not disclose the subject's identity.

2. Confidentiality Precautions: Confidentiality is an extension of the concept of privacy; it refers to the subject's understanding of, and agreement to, the ways identifiable information will be stored and shared. Identifiable information can be printed information, electronic information or visual information such as photographs. **What precautions will be used to maintain the confidentiality of identifiable information?**

Select all that apply:

Storing research data on password protected computers or in locked cabinets or offices

Participant identifiers will be stored separately from the coded, participant data

Other or additional details (specify):

3. Will photos, audio recordings, or video recordings, or medical images of participants be made during the study?

Yes No

If yes, describe the recording/images and what will become of them after creation (e.g., shown at scientific meetings, stored in the medical/research record, transcribed, erased, etc.):

4. How will study data and documentation be monitored throughout the study?

Select all that apply:

Periodic review and confirmation of participant eligibility

Periodic review of informed consent documentation

Periodic review of the transfer/transcription of data from the original source to the research record

Confirmation that all appropriate information has been reported to the sponsor, oversight agencies (such as the FDA), and/or IRB

Other additional details (specify):

5. Who will be the primary monitor of the study data and documentation?

Select all that apply:

Principal Investigator

Study Coordinator or Research Nurse

Other or additional details (specify):

Other or additional details (specify):

Sub-investigators

6. How often is study data and documentation monitoring planned (e.g., monthly, twice a year, annually, after N participants are enrolled, etc.)?

Annually

IRB_00075978**Created:** 8/9/2014 9:53 AM**IRB_00075978**

View: 6. Risks and Benefits

PI: [name]

Submitted: 8/20/2014

Title: Efficacy and safety of loteprednol 0.5% gel for routine prophylaxis after photorefractive keratectomy compared to prednisolone acetate 1% suspension and fluorometholone 0.1% suspension

6. Risks and Benefits

1. Describe the reasonable foreseeable risks or discomforts to the participants:

This study does not put study participants at any known increased risk beyond that normally assumed by patients undergoing photorefractive keratectomy outside the study, including but not limited to decreased vision, over-correction, under-correction, pain, glare, halos, dry eyes, infection, and corneal haze. The risk of topical steroid-related complications following photorefractive keratectomy, including elevated intraocular pressure, infection, and cataract formation, is assumed by all patients undergoing the procedure at our institution, as it is our routine standard practice to put patients on a tapering regimen of topical steroids post-operatively to decrease the risk of corneal haze.

2. Describe the potential benefits to society AND to participants (do not include compensation):

There may be no direct benefits to participants from their participation in this study. If no difference in efficacy or safety is detected between the two post-operative treatment regimens, this study will support the use of either steroid regimen in patients after PRK. If there is a major difference in the efficacy or safety of these two regimens, this could influence post-refractive surgery treatment practices.

3. Are there any costs to the participants from participation in research?

 Yes No

If yes, specify:

All subjects will be charged the research-discounted price for PRK (\$1200 per eye) and will be responsible for the cost of all necessary medications. Loteprednol is significantly more expensive than prednisolone and fluorometholone. Bausch and Lomb has unconditionally donated loteprednol 0.5% gel for this study, thus patients randomized to the loteprednol arm will be provided this medication without charge. Patients randomized to the prednisolone/fluorometholone arm will be responsible for paying for this medication, just as they would be were they not enrolled in the study.

4. Is there any compensation to the participants?

 Yes No

a. If yes, answer the following:

Specify overall amount:

b. Specify when participants will be paid (e.g. at each visit, at end of study, etc.):

c. If applicable, please specify payment by visit or other time interval (e.g. \$10 per visit, etc.):

d. If applicable, explain plan for prorating payments if participant does not complete the study:

IRB_00075978

Created: 8/9/2014 9:53 AM

IRB_00075978

PI: [name]

Submitted: 8/20/2014

View: 7. HIPAA

Title: Efficacy and safety of loteprednol 0.5% gel for routine prophylaxis after photorefractive keratectomy compared to prednisolone acetate 1% suspension and fluorometholone 0.1% suspension

7. HIPAA and the Covered Entity

1. **Does this study involve Protected Health Information (PHI) or de-identified health information?**

Yes No

a. **Select the method(s) of authorization that will be used:**

(Consent and) Authorization Document

b. **Will PHI be disclosed outside the Covered Entity?**

Yes No

Does this study involve any of the following:

2. **The investigational use of a drug?**

Yes No

3. **The investigational use of a medical device?**

Yes No

4. **Is this an investigator-initiated drug or device trial lead by the Principal Investigator?**

Yes No

5. **Exposure to radioisotopes or ionizing radiation?**

Yes No

6. **A Humanitarian Device Exemption (HDE)?**

Yes No

7. **Genetic testing and/or analysis of genetic data?**

Yes No

8. **Creating or sending data and/or samples to a repository to be saved for future research uses?**

Yes No

9. **Are you:**

- Collecting samples of blood, organs or tissues from participants for research purposes;
- Introducing Recombinant or Synthetic Nucleic Acids (e.g. viral vectors, oligonucleotides) or cells containing recombinant nucleic acids (e.g. CAR-T) into participants; OR
- Introducing other biological materials (e.g. bacteria, viruses) into participants.

Yes No

10. Does this study involve any of the following?

- Cancer Patients
- Cancer Hypothesis
- Cancer risk reduction
- Cancer prevention

 Yes No

11. Any component of the Center for Clinical and Translational Science (CCTS)?

 Yes No**The Clinical Services Core (CSC)?** Yes No

IRB_00075978**Created:** 8/9/2014 9:53 AM**IRB_00075978**

View: 8. Resources & Responsibilites

PI: [name]

Submitted: 8/20/2014

Title: Efficacy and safety of loteprednol 0.5% gel for routine prophylaxis after photorefractive keratectomy compared to prednisolone acetate 1% suspension and fluorometholone 0.1% suspension

8. Resources and Responsibilities

1. * State and justify the qualifications of the study staff:

[name] specializes in the medical and surgical treatment of corneal and anterior segment eye diseases. His expertise includes corneal transplantation, cataract surgery, and vision correction using lasers, intraocular lenses, and conductive keratoplasty.

[name] is a board certified Ophthalmologist specializing in the medical and surgical treatment of corneal and anterior segment diseases at the Moran Eye Center.

[name] is a fellow in cornea and refractive surgery at the Moran Eye Center and works under the supervision of [name].

2. * Describe the training that study staff and investigators will receive in order to be informed about the protocol and understand their research-related duties and functions:

All investigators have completed the CITI human subjects training. The PI will train the sub-investigators on the protocol.

3. * Describe the facilities where the research activities will be performed (e.g. hospitals, clinics, laboratories, classrooms/schools, offices, tissue banks, etc.).

All resources required to implement the study protocol are available at the Moran Eye Center clinics. Clinical care services at the Moran Eye Center include three fully equipped operating rooms, minor procedure rooms, 25 examination rooms, a laser suite, an optical shop, and a pharmacy.

4. * Describe the medical or psychological resources available at this site (and other participating sites, if applicable) that participants might require as a consequence of the research. If not applicable, please state.

The investigators will be available to answer any questions or discuss any concerns the participants have. [name] has the expertise and medical resources to appropriately handle any medical consequences of the research study.

IRB_00075978**Created:** 8/9/2014 9:53 AM**IRB_00075978**

View: 9. Documents and Attachments

PI: [name]

Submitted: 8/20/2014

Title: Efficacy and safety of loteprednol 0.5% gel for routine prophylaxis after photorefractive keratectomy compared to prednisolone acetate 1% suspension and fluorometholone 0.1% suspension

Documents and Attachments

If any of your documents (such as investigational brochures, sponsor protocols, advertisements, etc.) are not available in an electronic format, please scan and save them as PDF files or contact our office for assistance.

Naming Documents: Please use the title field to clearly indicate the content of each form. The name you enter will be listed on your approval letter. Use names that will differentiate from earlier versions.

Examples:

Consent Document Control Group 04/14/05
 Consent Document Treatment Group 4/14/05
 Sponsor Protocol 04/14/05 Version 2
 Assent Document(Highlighted Changes)

Apple/Macintosh Users: MS Word documents must have a .doc file extension. See ERICA home page for instructions.

Print View: IRB Draft Protocol Summary

eProtocol Summary:

Name	Version	Date Created	Date Modified	Date Approved
There are no items to display				

Consent Documents, Consent Cover Letters, Consent Information Sheets, Consent Scripts, etc.:

Name	Version	Date Created	Date Modified	Date Approved
There are no items to display				

Parental Permission Documents:

Name	Version	Date Created	Date Modified	Date Approved
There are no items to display				

Assent Documents:

Name	Version	Date Created	Date Modified	Date Approved
There are no items to display				

VA Consent Documents:

Name	Version	Date Created	Date Modified	Date Approved
There are no items to display				

Surveys, Questionnaires, Interview Scripts, etc.:

Name	Version	Date Created	Date Modified	Date Approved
There are no items to display				

Full Protocol (company protocol, sponsor protocol, investigator-initiated protocol, etc.):

Name	Version	Date Created	Date Modified	Date Approved
There are no items to display				

Investigational Brochure (IB) for Investigational Drug or Drug/Device Package Insert:

Name	Version	Date Created	Date Modified	Date Approved
There are no items to display				
Literature Cited/References:				
Name	Version	Date Created	Date Modified	Date Approved
There are no items to display				
Principal Investigator's Scholarly Record (CV/Resume):				
Name	Version	Date Created	Date Modified	Date Approved
 [name] CV 04.09.2014.pdf(0.01)	0.01	7/14/2015 3:23 PM	7/14/2015 3:23 PM	
 [name](0.01)	0.01	2/21/2017 7:55 PM	2/21/2017 7:55 PM	
Faculty Sponsor's Scholarly Record (CV/Resume):				
Name	Version	Date Created	Date Modified	Date Approved
There are no items to display				
Other Stamped Documents:				
Name	Version	Date Created	Date Modified	Date Approved
There are no items to display				
Recruitment Materials, Advertisements, etc.:				
Name	Version	Date Created	Date Modified	Date Approved
There are no items to display				
Other Documents:				
Name	Version	Date Created	Date Modified	Date Approved
There are no items to display				

IRB_00075978**Created:** 8/9/2014 9:53 AM**IRB_00075978**

View: 12. Finish Instructions

PI: [name]

Submitted: 8/20/2014

Title: Efficacy and safety of loteprednol 0.5% gel for routine prophylaxis after photorefractive keratectomy compared to prednisolone acetate 1% suspension and fluorometholone 0.1% suspension

Finish Instructions

Finish Instructions

1. To view errors, select the "Hide/Show Errors" option at the top or bottom of the page. If you have errors on your application, you won't be able to submit it to the IRB.
2. Selecting the Finish button will NOT submit the application to the IRB. You MUST select the "Submit" option on the workspace once you've selected the "Finish" button.
3. If your study has a faculty sponsor: Once the PI submits the application, it will be sent to the faculty sponsor for final approval. The IRB cannot review the study until the faculty sponsor submits the application to the IRB.

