Hypothesis: Loteprednol 0.5% gel will perform similarly or better than a regimen of prednisolone acetate 1% and fluorometholone 0.1% in the prevention of visually significant postoperative corneal haze after photorefractive keratectomy (PRK) with a lower incidence of intraocular pressure elevation.

Objectives: We aim to conduct a prospective, randomized trial to compare the incidence of intraocular pressure rise and visually significant postoperative corneal haze after PRK with the use of loteprednol 0.5% gel compared to the use of earlier generation steroids, prednisolone acetate 1% suspension and fluorometholone 0.1% suspension.

Patients undergoing PRK will be assigned to 1 of 2 postoperative steroid regimens. Group 1 will use only loteprednol 0.5% gel, tapered off slowly based on clinical evaluations of the corneal healing response. Group 2 will use prednisolone acetate 1% suspension tapered down to a regimen of fluorometholone 0.1% which will then be tapered off based on clinical evaluations of the corneal healing response. If no difference in efficacy or safety is detected between these two regimens, this study will support the use of either steroid regimen in patients after PRK. If there is a major difference in the efficacy or safety of these two regimens, this could influence post-refractive surgery treatment practices.

7. Is this a multi-site study, where more than one site needs IRB approval?

Yes No

8. Background and Introduction:

In photo-ablation procedures, an excimer laser is used to sculpt corneal tissue to correct refractive error. During PRK, the surface epithelium is removed and the laser energy is applied to reshape the underlying corneal stroma. This procedure is FDA approved and used widely. Corneal haze is a well known and a potentially vision threatening postoperative complication of PRK. Topical ophthalmic corticosteroids are routinely prescribed by most surgeons postoperatively to help prevent this complication.

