Prior to surgery, patients will be randomly assigned to one of two postoperative steroid regimens. Group 1 will use loteprednol 0.5% gel in both eyes, starting at a frequency of four times per day for the first week and then tapered off based on clinical judgement of the corneal healing response. Group 2 will use prednisolone acetate 1% suspension in both eyes, starting at a frequency of four times per day for the first week, then tapered down to a regimen of fluorometholone 0.1% suspension, which will then be tapered off based on clinical judgement of the corneal healing response.

All surgical procedures will be performed according to the standard of care and the surgeons' standard practices. The study outcome measures are standard of care for pre-operative and post-operative evaluation of refractive surgery patients.

The primary outcome measure will be intraocular pressure at each study time point. Secondary outcomes will be grade of corneal haze, manifest refraction, best corrected visual acuity, and uncorrected visual acuity.

Study outcome measures will be evaluated for each treated eye of each subject at each study time point. Routine clinical management may be altered if the intraocular pressure is elevated sufficiently to require medical intervention, if there is significant postoperative corneal haze, or if there are other postoperative complications. In these situations, additional IOP lowering drops may be added or the steroid decreased, changed, or increased, based on the clinical picture and physician judgement. Additional examinations between study time points may be performed as necessary according to the surgeon's usual care, but will not be considered part of the study data. Patients have the right to withdraw at any time and future medical care will not be influenced by their lack of participation.

If enhancement surgery is deemed necessary and performed during the one-year post-operative period, study data collection will end for that eye at the time of the enhancement. All prior data collected will still be included in the statistical analysis and if only one eye requires enhancement, data collection will continue on the fellow eye until the last planned study time point.

Eyes will be evaluated with the following procedures:

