Yes No

If no, list the procedures that are performed for research purposes only (non-standard or non-standard of care procedures):

Only data collection and analysis are for research purposes only. All other procedures are within the standard of care.

8. Is there a safety monitoring plan for this study?

Yes No

9. Provide a summary of the statistical methods, data analysis, or data interpretation planned for this study. Factors for determining the proposed sample size (e.g., power) should be stated.

Standard statistics will be calculated and used to describe the two treatment groups in terms of all study variables: intraocular pressure, grade of corneal haze, manifest refraction, best corrected visual acuity, and uncorrected visual acuity. Statistics will be compiled for each variable at the study time points listed in the data collection protocol. Patients withdrawn from the study prior to surgery will not be included in the data analysis and will be replaced in the enrollment group. For eyes that require enhancement surgery, only data collected prior to the enhancement surgery will be included in the statistical analysis.

Prior studies have considered intraocular pressure elevation of greater than or equal to 10 mm Hg above baseline clinically significant. A prior study of healthy volunteers demonstrated an incidence of IOP elevation > 10 mm Hg of 1.95% in patients using loteprednol eye drops versus 7.48% in patients using dexamethasone eye drops [1]. Using these expected proportions, an alpha of 0.05, and a power of 80%, we would need a sample size of 230 patients (460 eyes). In order to account for about 10% dropout, we intend to enroll 250 patients in the study, 125 in the loteprednol arm and 125 in the prednisolone and fluorometholone arm.

IRB_00075978

Created: 8/9/2014 9:53 AM

IRB_00075978

PI: [name]

Submitted: 8/20/2014

View: 4.2 Consent Process

Title: Efficacy and safety of loteprednol 0.5% gel for routine prophylaxis after photorefractive keratectomy compared to prednisolone acetate 1% suspension and fluorometholone 0.1% suspension

Consent Process

1. The following investigators and internal staff will obtain consent (as indicated on the Study Location and Sponsors Page):

[name] University of Utah

[name]

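### The stated primary outcome is IOP at each visit, but the sample size and its 80% power are for the proportion of patients with an IOP rise of about 10 mm Hg, which the plan never designates as an outcome

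*Combined protocol and SAP*

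**What the plan says.** In section 4 (Study Information), item 6: "The primary outcome measure will be intraocular pressure at each study time point". The schedule in the same item gives a pre-operative reading and six post-operative ones (week 1 and months 1, 2, 3, 6 and 12). On the unit: "Study outcome measures will be evaluated for each treated eye of each subject at each study time point". Randomisation is by patient, with the same regimen in both eyes.

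The Hypothesis is worded differently. It expects loteprednol to do similarly or better on haze "with a lower incidence of intraocular pressure elevation". The Objectives set out "to compare the incidence of intraocular pressure rise and visually significant postoperative corneal haze after PRK".

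Item 9 of section 4 holds the statistical plan. Its analysis text begins: "Standard statistics will be calculated and used to describe the two treatment groups in terms of all study variables". It names no test. For the sample size it first says: "Prior studies have considered intraocular pressure elevation of greater than or equal to 10 mm Hg above baseline clinically significant". It then cites a study of healthy volunteers that "demonstrated an incidence of IOP elevation > 10 mm Hg of 1.95% in patients using loteprednol eye drops versus 7.48% in patients" using dexamethasone, and concludes: "Using these expected proportions, an alpha of 0.05, and a power of 80%, we would need a sample size of 230 patients (460 eyes"). Planned enrolment is 125 per arm, 250 in all.

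**The concern.** A primary outcome and its sample size should concern the same quantity. Here the outcome is a pressure reading at each visit, while the calculation concerns a yes/no event. That event is in neither the primary nor the secondary outcome list, and no window says whether it may occur at any visit or at one.

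The two quantities can give different answers. Item 6 allows pressure-lowering drops or a change of steroid once pressure is raised. A patient who had the event may therefore show ordinary readings at later visits, and a comparison of visit-level IOP could miss the difference in incidence that the Hypothesis is about.

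The interpretation is also at stake. The Objectives and section 6 (Risks and Benefits) say that finding no difference will support either regimen. That reading depends on knowing which comparison was made and with what power. For the stated primary outcome, neither is known. Two analysts following this plan could report different primary results, and the choice could be made after the data are seen.

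**Working it through.** **Inputs from item 9.** p1 = 0.0195, p2 = 0.0748, alpha 0.05, power 80%, 230 patients (460 eyes), 125 enrolled per arm. The number of sides is not stated; two-sided reproduces the figure.

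**1. Reproducing the plan's figure.** Pooled two-proportion formula, no continuity correction:

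n per group = [1.960·√(2·p̄(1−p̄)) + 0.842·√(p1(1−p1)+p2(1−p2))]² / (p2−p1)²

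with p̄ = 0.04715 and p2−p1 = 0.0553:

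- 1.960 × 0.2998 = 0.5875
- 0.842 × 0.2972 = 0.2501
- (0.8376)² / (0.0553)² = 229.4, so 230 per group, 460 units, power 80.1%.

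The plan's 460 is therefore the size for the binary event. The plan calls these units eyes. It does not say whether eyes were taken as independent or whether 230 per group was read as the total number of patients.

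**2. Power for the stated primary outcome.** This needs an SD and a target difference for IOP, and the documents give neither. What can be shown is the detectable difference at one named visit, one value per patient, two-sided 0.05, 80% power: (1.960 + 0.842)·√(2/N).

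- N = 115 per arm (230/2): 2.802 × 0.1319 = 0.37 SD
- N = 125 per arm: 2.802 × 0.1265 = 0.35 SD

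At assumed SDs of 2 to 4 mm Hg this is 0.74 to 1.48 mm Hg (115) or 0.71 to 1.42 mm Hg (125). Whether that is adequate depends on a target the plan does not state.

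**3. Power if the sized event becomes primary, analysed per patient (either eye).** If the quoted rates are per patient, expected events at 115 per arm are 115 × 0.0195 = 2.2 and 115 × 0.0748 = 8.6.

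| Patients per arm | Normal approximation | Fisher's exact test |
|---|---|---|
| 115 | 51% | 38% |
| 125 | 54% | 42% |

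If the rates are per eye, P(either eye) = 2p − [p² + ρp(1−p)], where ρ is the between-eye correlation. The documents give no ρ, so it is assumed here. Normal approximation:

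| ρ | 0 | 0.25 | 0.5 | 0.75 | 0.9 | 1 |
|---|---|---|---|---|---|---|
| 115 per arm | 80% | 74% | 67% | 60% | 54% | 51% |
| 125 per arm | 83% | 77% | 71% | 63% | 58% | 54% |

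**4. The same event per eye, clustered on patient.** With effective n = 2N/(1+ρ) per arm, 115 patients give 80%, 63%, 53% and 51% at ρ = 0, 0.5, 0.9 and 1.

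Steps 3 and 4 show what the restated power may look like. The loss comes from the unit of analysis and would arise even if the event had been named as primary from the start.

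**The case against.** The best defence is that item 6 names the measurement and its schedule, while the Hypothesis, Objectives and item 9 name the comparison: a rise from baseline, about 10 mm Hg, with rates and alpha. The intended endpoint is then evident, and so is the eye as the unit of evaluation. Much of this stands. The difference between at least 10 and above 10 is also small in itself, since one phrase describes prior studies and the other one study's rates. But inferred intent does not supply a time window, a test or a designation, and an analyst who follows item 6 literally would analyse something else.

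A reader might go further and infer that the plan sets up six co-primary tests with an inflated error rate. The documents do not support that. Measuring at each time point can describe one repeated outcome, and item 9 plans descriptive statistics without naming any test.

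Two objections to the remedy also hold. With about 2 versus 9 expected events, the normal approximation is optimistic and a model for clustered eyes would be fragile. And the quoted rates come from healthy volunteers with a comparator used in neither arm and no follow-up period given, so they are weak support for an event counted over 12 months.

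**Conclusion.** The concern holds. The stated 80% power belongs to the proportion with an IOP elevation above 10 mm Hg and cannot be transferred to IOP at each study time point. Power for the stated primary outcome is undefined.

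Two stronger conclusions are tempting and do not follow. The first is that the trial is underpowered for its stated primary outcome: without an SD and target difference the documents cannot show this, and 0.35 to 0.37 SD at one visit may be ample. The second is that the mismatch itself cuts power to 51–54%. That fall comes from analysing patients rather than independent eyes. It also assumes that the quoted rates are per patient; if they are per eye, the range is 80% to 51% at 115 per arm and 83% to 54% at 125, depending on the assumed correlation.

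This should be settled before outcome data are examined, because it decides what the main result is.

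**What to change.** Designate the sized event as the single primary endpoint: a rise from that eye's pre-operative IOP beyond one stated threshold, at any scheduled visit through month 12 or until enhancement of that eye. Use the same threshold in the sample size. The quoted rates are for above 10 mm Hg; if at least 10 is chosen, restate the expected rates for it. Compare the arms once at two-sided 0.05 and make IOP by visit secondary.

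Because patients are randomised and both eyes get the same regimen, analyse either per patient (event in either eye) with a test suited to few events, or per eye with clustering on patient. Classify patients who leave early, and eyes that leave at enhancement, on the scheduled readings obtained. This treats unobserved follow-up as event-free, so add a sensitivity analysis that censors them. Say also how an eye is counted if its treatment was changed for pressure before it crossed the threshold.

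Restate the power at the planned 250 for the chosen unit and test. Say that the quoted rates are assumptions for this window and comparator.

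The alternative is to keep IOP as primary with one named contrast at one visit and its own SD, target difference and power. That would answer a question about mean pressure, not incidence.

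The cost is a text change and a restated power figure. All the readings are already scheduled, and no larger enrolment is asked for. The downsides are that the stated power becomes less favourable, and that a rise seen only at an unscheduled examination does not count, since item 6 excludes those examinations from the study data.
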